implementation on sub-anesthetic doses of intravenous ketamine as augmenting strategy of standardized, manually-driven PE in PTSD (*Figure 7*). For this purpose, we aim to: **1) clarify research hypotheses on the efficacy, safety and tolerability of this MEP approach; 2) assess the acceptability of methods and instruments to participants; 3) identify potential barriers to subsequent study completion, and 4) obtain estimates of means, standard deviation and 95% confidence intervals on outcome measures as well as the expected rates of missing data and participant attrition.** We estimate that analysis of data obtained from participation of 10 patients will provide responses to our scientific aims. Participants will be male and female veterans (18 to 75 years old) of any era or military background diagnosed with PTSD. Potential participants will be recruited from Mental Health clinics and screened for eligibility using a two-stage process (phone/chart review, followed by interview). Those who meet eligibility criteria will complete baseline assessment one week prior to starting treatment. Then, treatment will consist of 1) 3-week ketamine-PE phase composed by weekly single intravenous ketamine (0.5 mg/kg for 40 minutes) followed within 24 hrs. by PE session; and 2) ketamine-free PE phase from week 4 through 12. After PE is completed (session 12), patients will be assessed during a 2-month follow-up period at various time points. We estimate that 10 veterans will reach time point for primary outcome measure (CAPS score at week 12) and will be considered for primary analysis. Independent evaluation of PTSD, cognitive function, depression, anxiety and other potential covariates (i.e., pain) will be ascertained at baseline, at several time points during treatment, and at follow-up.

D.1.1. Design Considerations: As with any pilot study, several factors have been considered in the design of this proposal. The goal is to provide a design that is feasible, efficient, and above all, able to answer study aims. Some of the possible alternative designs, and reasons we did not select them, are listed.

Table 2. Considerations and Rationale for Choosing the Current Design

Consideration	Rationale

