Doses of ketamine	Several studies(Xu et al., 2016) have shown that ketamine doses at 0.5 mg/kg have higher antidepressant and similar adverse effects than lower (e.g., 0.1 mg/kg or 0.2 mg/kg) or higher (e.g., 1.0 mg/kg) doses, respectively. The presence of an inverted U-shaped relationship between dose and response is supported by higher doses of ketamine having no effect inducing mTOR activation(Li et al., 2011). Moreover, a single ketamine at 0.5 mg/kg, and not at 0.2 mg/kg, showed procognitive effects by improving sustained attention and cognitive response control among 71 patients with TRD (Chen et al., 2018). Studies(Feder et al., 2014) (Albott et al., 2018) in PTSD using a single as well as repeated ketamine infusions were dosed at 0.5 mg/kg with rapid, safe but short-lived reduction of PTSD symptom severity.
Interval between ketamine and PE	Ketamine has an elimination half-life is 186 minutes(Clements, Nimmo, & Grant, 1982) with temporary dissociative/psychotomimetic effects observed at doses of 0.5 mg/kg between 40 and 120 minutes posttreatment, which resolve within 240 minutes of administration(Zarate et al., 2006) (Murrough et al., 2013). However, ketamine's putative therapeutic mechanism (e.g., sustained increase in prefrontal synaptic connectivity (Abdallah et al., 2016) (Duman, Aghajanian, Sanacora, & Krystal, 2016)) persists beyond its bioavailability(Duman & Aghajanian, 2012). These lasting physiological brain changes, which is reached within 24 hrs. of treatment, have proved to be a therapeutic window to enhance the outcomes of psychological interventions in pre-clinical and clinical studies (i.e., extinction learning in animal PTSD (Girgenti et al., 2017) model and CBT in OCD(Rodriguez et al., 2016), respectively). Studies in TRD suggested that the peak of antidepressant effects to ketamine occur 24 hours after administration (Zarate et al., 2006)(Zarate et al. 2006a) (Mathew et al., 2010). Moreover, this notion of peak of efficacy following an intravenous ketamine administration is further supported by the temporal overlap of subacute functional network modulation after 24 hours reported by neuroimaging studies (Scheidegger et al., 2012) (Murrough et al., 2015) .

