D.5.1. Eligibility and Baseline Assessment: The Eligibility and Baseline Assessment (EBA) will be accomplished during 1-2 visits over a 7 -day period prior to starting treatment. It will take a total of 3 hours. Provisional diagnosis of PTSD and its severity would be obtained by PCL-5 score >33 . The CAPS-5 would be then administered to establish PTSD diagnosis. The M.I.N.I. International Neuropsychiatric Interview (M.I.N.I. 6.0)(Sheehan et al., 1998) will be used for psychiatric evaluation to confirm the absence of exclusionary diagnoses. Lack of moderate/severe cognitive impairment will be ascertained with an MMSE score ≥ 28 . Evaluation of exclusionary criteria involving unstable medical illnesses will be based on brief physical examination, medical record review by study M.D. in consultation with on-site study

anesthesiologist, basic metabolic laboratory tests, and ECG. A urine pregnancy, if applicable, and drug screen will also be obtained. Secondary outcomes at baseline will include cognitive function (CogState), severity of depressive symptoms (MADRS), levels of anxiety (Beck Anxiety Inventory-BAI), suicide risk (Columbia- Suicide Severity Rating Scale- C-SSRS), pain intensity (Numeric Rating Scale-NSR for pain), clinical impression of illness severity (Clinical Global Impression-CGI) quality of life (World Health Organization Quality of Life-Brief-WHOQOL-BREF), and expectation of treatment (CEQ).

D.5.2. Treatment Assessment: The research staff will measure PTSD symptoms severity by administering the CAPS-5 at weeks 4, 12 and 2-month follow-up. Secondary outcomes that includes cognitive function, anxiety, depression, pain, suicide, and general side effects (Patient Rated Inventory of Side Effects- PRISE/ Frequency, Intensity, and Burden of Side Effects Rating-FIBSER) will be obtained 24 hrs. post-ketamine and prior to PE session at week 1, 2, and 3 (ketamine-PE phase). We will administer rating scales again at week 4, 6, 8, and 12 (ketamine-free phase), and at 2-month follow-up. Fear activation and extinction during PE sessions would be measured by the Subjective Units of Distress Scale (SUDS).

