D.6.4. Side Effects Measures: We will monitor side effects during intervention and at follow-up visits. The **PRISE** (Rush et al., 2004) assess for the last 7 days the side effects in the following symptom domains; Gastrointestinal, Heart, Skin, Nervous System, Eyes/Ears, Genital/Urinary, Sleep, Sexual Functioning, and Other. Each domain has multiple symptoms which can be endorsed. The PRISE is used in combination with **FIBSER** (Wisniewski, Rush, Balasubramani, Trivedi, & Nierenberg, 2006) which rates the intensity, frequency and overall burden due to side effects in a 7-point Likert-type scale. During ketamine infusions, we will assess potential side effects by 1) the **CADSS** (Bremner et al., 1998), a clinician-administered tool validated in healthy subjects and patients with PTSD and designed to measure present-state perceptual, behavioral, and attentional alterations occurring during dissociative experiences; 2) the four-item positive symptom subscale of the **BPRS** (Zanello, Berthoud, Ventura, & Merlo, 2013) a clinician-rated tool that assess change in severity of psychopathology consisting of suspiciousness, hallucinations, unusual thought content, and conceptual disorganization; and 3) the **YMRS** (Young, Biggs, Ziegler, & Meyer, 1978), item #1 to evaluate possible manic symptoms. Finally, the **Modified Aldrete score system** (mAldrete)(Aldrete, 1995) is a set of criteria commonly used to assess transition from anesthesia to recovery. Numeric scores of 0, 1, or 2 are assigned to motor activity, respiration, circulation, consciousness, and SpO₂ level for a maximal score of 10. A score ≥ 9 is required for discharge from post-anesthesia care unit.

6.7. Data Analysis Plan.

6.7.1. Sample Details: *We propose a sample of 10 patients in this proof-of-concept pilot study.*

6.7.2. Data Collection: Study data will be collected and managed using VA REDCap (Research Electronic Data Capture) hosted behind the VA firewall on a VINCI server. REDCap is a secure, web-based application designed to support data capture for research studies, providing 1) an intuitive interface for validated data entry; 2) audit trails for tracking data manipulation and export procedures; 3) automated export procedures for seamless data downloads to common statistical packages; and 4) procedures for importing data from external sources.

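### PRISE looks back 7 days but is given 24 hours after each weekly infusion, so six-sevenths of each form's recall window precedes the infusion it is filed under

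*Combined protocol and SAP*

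**What the plan says.** D.1 gives the treatment rhythm for the first three weeks: "weekly single intravenous ketamine (0.5 mg/kg for 40 minutes) followed within 24 hrs. by PE session". D.5.2 places the secondary measures, including general side effects by PRISE/FIBSER, relative to that rhythm: they "will be obtained 24 hrs. post-ketamine and prior to PE session at week 1, 2, and 3 (ketamine-PE phase"). It continues: "We will administer rating scales again at week 4, 6, 8, and 12 (ketamine-free phase), and at 2-month follow-up".

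D.6.4 states that PRISE serves to "assess for the last 7 days the side effects in the following symptom domains". FIBSER is paired with it, "which rates the intensity, frequency and overall burden due to side effects in a 7-point Likert-type scale", but no recall period is given for FIBSER.

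Neither instrument is taken before treatment. The baseline list in D.5.1, which opens "Secondary outcomes at baseline will include cognitive function (CogState), severity of depressive symptoms (MADRS), levels of anxiety", does not include them, and Table 5 marks them under treatment and follow-up only. No altered recall stem and no rule for assigning a reported symptom to an infusion is stated for PRISE. D.6.3, by contrast, says that the PCL-5 time frame was changed for this study.

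**The concern.** The recall period and the visit do not match. A 7-day form completed one day after a weekly infusion describes mainly the week before that infusion. At week 1 that is time before any ketamine, and without a baseline form those symptoms cannot be recognised as pre-existing. At weeks 2 and 3 it is mainly the tail of the previous infusion. The days after infusion 3 are left to week 4, under a label that says ketamine has stopped.

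The order within the week adds to this. Each form precedes that week's PE session, so the week-1 form contains no exposure to ketamine and PE together. Imaginal exposure starts in session 3 (D.4.2, Table 2), after the week-3 form. The days that follow both infusion 3 and the first imaginal exposure are therefore rated first at week 4. This is the period of interest if the symptom exacerbation that A.6.2 and Table 2 cite after imaginal exposure occurs here.

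D.1 names safety and tolerability of the combined approach among the first of its aims, and section 6.7.3 plans descriptive summaries at key assessments to refine a later trial. Tables of general side effects by visit or phase would carry the misalignment unless it is corrected or explained.

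**Working it through.** The plan gives no figure to reproduce. The check is an overlap of time windows.

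**Inputs.** Three weekly infusions (D.1), taken as days 0, 7 and 14. Forms 24 h after each (D.5.2), so days 1, 8 and 15. PRISE recall of 7 days (D.6.4). The week-4 form is assumed to fall on day 22, one week after the week-3 form, because no visit windows are stated.

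**Formula.** A form on day v covers v − 7 to v. Its overlap with an interval a to b is min(v, b) − max(v − 7, a), or zero if that is negative.

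| Form | Window (days) | Content |
|---|---|---|
| Week 1 | −6 to 1 | 6 days before any ketamine, 1 day after infusion 1 |
| Week 2 | 1 to 8 | 6 days after infusion 1, 1 day after infusion 2 |
| Week 3 | 8 to 15 | 6 days after infusion 2, 1 day after infusion 3 |
| Week 4 | 15 to 22 | 6 days after infusion 3, 1 day later than that week |

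- Share of the week-1 window after dosing: 24/168 h = 14.3%. Share before dosing: 6/7 = 85.7%.
- The three ketamine-phase forms recall 21 days: 6 before treatment and 1 + 6 + 1 + 6 + 1 = 15 after an infusion.
- The three post-infusion weeks also total 21 days. The missing 6 (6/21 = 28.6%) are reported at week 4.
- If the form is completed earlier than 24 h, the part of the window before that week's infusion grows: 6.5 of 7 days at a 12 h gap and 6.83 of 7 at 4 h.

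**From time to effects.** Table 2 gives two figures on time course. On dissociative and psychotomimetic effects: "which resolve within 240 minutes of administration". On clearance: "Ketamine has an elimination half-life is 186 minutes".

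- 240/1440 = one-sixth of the first 24 h, so effects with that course lie wholly inside the day that belongs to the correct form.
- At 24 h, 1440/186 = 7.74 half-lives have passed, and 2^(−7.74) ≈ 0.5% of the drug remains.

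The documents give no onset times for the other PRISE domains. As an illustration, assume exponential onset with mean τ days, truncated at 7 days. The share arising in the first 24 h is (1 − e^(−1/τ)) / (1 − e^(−7/τ)).

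| Assumed onset | Share in first 24 h |
|---|---|
| τ = 4 h | 99.8% |
| τ = 12 h | 86.5% |
| τ = 1 day | 63.3% |
| τ = 2 days | 40.6% |
| τ = 3 days | 31.4% |
| Uniform over 7 days | 14.3% |

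The share falls below half only when τ exceeds about 1.46 days. Nothing in the documents shows that it does.

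**Check of the fix.** Seven-day forms on days 7, 14 and 21 cover 0 to 7, 7 to 14 and 14 to 21. Each window is exactly the week after one infusion.

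**The case against.** The case for leaving the schedule alone has several strong parts.

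- *Acute effects are on the right form.* They fall within 24 h. CADSS, BPRS+, YMRS and vital signs also follow each infusion, with a recovery score required before discharge (D.4.1, Table 4). This stands for dissociative, psychotic and manic symptoms. It does not settle the matter for domains such as sleep, gastrointestinal or sexual functioning, which PRISE covers and those scales do not.
- *Nothing is lost.* On the assumed schedule the forms run on without a gap, so every post-infusion day is rated once. This stands: the problem is where a symptom is filed, not whether it is recorded.
- *No analysis depends on it.* Section 6.7.3 is descriptive and specifies no per-infusion attribution or comparison between phases. The safety panel in 6.7.4 reviews all adverse events without a phase split. This stands, and it is the main reason for the low severity.
- *The fix does not isolate ketamine.* Each realigned week still contains a PE session and homework. That is true, but the stated aim concerns the combination.

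A reader might infer more than the documents allow. Six-sevenths of the window does not mean that most side effects are misfiled, because it counts days and not events. Nor can an infusion's effects be filed to time before treatment. At week 1 the error runs the other way, from pre-existing symptoms to infusion 1. Untreated days do not dilute the first rating either: PRISE items are endorsed, not averaged over days, so a symptom in the last 24 h can be reported whatever came before. The week-4 label does not charge ketamine effects to PE alone, since there is no PE-alone arm. Finally, the 7-day period is stated for PRISE only and cannot be assumed for FIBSER.

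**Conclusion.** The mismatch is real and minor. PRISE's 7-day recall does not fit a visit 24 h after a weekly infusion. The week-1 form is 6/7 pre-treatment with no baseline form to set against it. Effects arising on days 2-7 after infusions 1 and 2 go on the next infusion's form, and those after infusion 3 go on the week-4 form.

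The day counts rest on exact 7-day spacing, a 24 h gap and a week-4 form on day 22. How many side effects are affected cannot be determined, because it depends on onset times that the documents do not give. The general side-effect description by visit or phase is blurred. The infusion-day safety data are not affected, and no efficacy result is touched. In a 10-patient descriptive pilot this warrants a cheap correction and no more.

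**What to change.** 1. At the 24-hour visits in weeks 1-3, ask PRISE/FIBSER with the stem *since the infusion*.
2. Give the 7-day PRISE form at the pre-infusion assessment of infusions 2 and 3, when patients are already on site (Table 4), and 7 days after infusion 3. The week-4 form can serve as the last of these if it is timed to that day.
3. In summaries by visit or phase, count the rating that covers the week after infusion 3 as ketamine-phase exposure.
4. State FIBSER's recall period.

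The cost is a revised visit schedule, two short extra self-report forms at existing visits and a modified recall stem. The PCL-5 shows that this protocol accepts a changed time frame, but the guidance it cites is specific to the PCL, so the altered PRISE/FIBSER stem should be reported as a modification. If the schedule cannot be changed, a sentence in the analysis section saying which days each form covers would deal with most of the problem. Adding a baseline form is a separate matter: it would help to identify pre-existing symptoms but would not realign the windows.

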
 1. Male or female Veterans aged 18-75 years old. 2. Diagnosis of chronic (minimum of three months) PTSD (Clinician-Administered PTSD Scale for DSM-5 -CAPS-5 score >33). 3. Voluntarily eligible to participate in PE. 4. Severity of PTSD symptoms defined by PCL-5 >33. 5. Psychotropic medications on stable doses (no dosing adjustments/changes for ≥ 4 weeks; ≥ 6 weeks for fluoxetine) prior to beginning of the study. 	
 1. Unwillingness/unable to sign informed consent. 2. Previous or current participation in trauma-exposed therapy and/or ketamine treatment. 3. Evidence of mental retardation, pervasive developmental disorder and/or moderate/severe cognitive impairment (MMSE scores ≤ 27). 4. Any unstable medical or non-psychiatric CNS condition. 5. Lifetime history of psychosis-related disorder, bipolar disorder I or II disorder, or any condition other than PTSD judged to be the primary presenting psychiatric diagnosis. 6. Moderate to severe traumatic brain injury (mental status change or loss of consciousness > 30 min; Glasgow Coma Scale < 13; post-traumatic amnesia > 24 hours; visible lesion on CT/MRI brain scan). 7. Active alcohol/illicit substance use disorder within 6 months of initial assessment; presence of illicit drugs by positive urine toxicology. 8. For women: pregnancy (confirmed by lab test), initiation of female hormonal treatments within 3 months of screening, or inability/unwillingness to use a medically accepted contraceptive method during the study. 9. Imminent risk of suicidal/homicidal ideation and/or behavior with intent and/or plan

D.3.2. Feasibility of recruitment: The study will recruit 10 Veterans over 12 months. In the last 12 months, 289 Veterans were diagnosed with PTSD and 114 have received at least 02 PE sessions at the MVA. While we do not anticipate any difficulties, we could expand recruitment to satellite clinics from MVA Health Care System.

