D.5.3. Follow-up Assessment: Following completion of treatment, participants will attend Post-Treatment Assessment monthly for 2 months (total of 02 follow-up visits). Each visit will take about 2 hours. Follow-up assessments will involve self-report for PTSD symptoms (PCL-5), cognitive assessment (CogState), depressive symptom severity (MADRS), clinical impression of illness severity and improvement (CGI), as well as self-reported measures of pain intensity (NRS for pain), level of anxiety (BAI), suicide risk (C-SSRS), general adverse events (PRISE/FIBSER) and quality of life (WHOQOL-BREF). The CAPS-5 will be administered once at 2-month follow-up.

Table 5: General Assessment Schedule

Construct	Measure	Eligibility and Baseline Assessment	Treatment Assessments	Follow-Up Assessment
		1-2 weeks	Week 1 to 12	2 months
Primary Outcome Measure				
PTSD symptoms	CAPS-5	X	X	X
Interview Based Assessments				
Decision-making capacity	Dysken Screening Tool	X		
PTSD severity	PCL-5	X	X	X
Diagnostic interview for comorbid conditions	M.I.N.I.	X		
Rule-out moderate/severe cognitive impairment	MMSE	X		
Infusion Safety Measures				
Physical Exam/ECG/Pregnancy test/Urine toxicology		X		
Recovery from infusion	mAldrete		X	
Side Effects (dissociative, psychotogenic, and manic symptoms)	CADSS, BPRS+, YMRS		X	
Secondary Outcome Measures				
Subjective units of distress (a proxy for extinction)	SUDS		X	
Cognitive function	CogState	X	X	X
Depressive Symptoms	MADRS	X	X	X
Suicide Risk	C-SSRS	X	X	X
Anxiety Symptoms	BAI	X	X	X
Pain Intensity	NRS	X	X	X
Quality of Life	WHOQOL-BREF	X	X	X
General Adverse Events	PRISE/FIBSER		X	X
Global Rating of Illness Severity and Improvement	CGI	X	X	X
Credibility/Expectation of Outcome Treatment	CEQ	X		

D.5.4. Independent Evaluation Integrity: The PI will oversee assessment core to ensure that independent evaluators will 1) undergo standardized training in all assessment instruments, 2) demonstrate reliability of

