6.7.3. Data Analysis: The data analyses will be performed by [name], Co-I on this project. Each subject will be assessed for the primary outcome variable (CAPS-5 score) at baseline (1-2 weeks prior to starting the intervention), week 4, and at the end of PE treatment (week 12). *Statistical analysis for this study will be essentially descriptive in nature. We will assess means, standard deviations, and 95% confidence intervals in symptoms at key assessment points. We will also examine distribution of missing data. In addition to the CAPS-5, we will also examine change in our secondary measures (PCL-5, CogState, MADRS, etc.), again these analyses will be descriptive in nature and will be used to refine our RCT proposal.*

6.7.4. Data Safety.

After the recruitment of 6 subjects, an independent, 3-person panel of physicians and researchers will conduct a reassessment of the risks and benefits to study participants. This panel will review all adverse events for severity and frequency.

6.8. Anticipated potential problems and alternative strategies.

The research infrastructure and SOPs to run ketamine infusions, and a well-established PTSD service are currently in place at MVA to assure timely start-up within 3 months. However, possible problems and solutions during execution of the study might be: 1) Slow recruitment/enrollment: We cautiously propose recruiting about 10 veterans aim to complete the primary outcome for our study. Nevertheless, if recruitment is slow, we would expand to include recruitment from satellites clinics within the Minneapolis VA Health Care System. In addition, we could reach out the Veteran's population served at the St. Cloud VA Health Care System (SCVAHCS) (see. 6.3.2. Feasibility of recruitment. 2) Dropouts and missing data: In our own sample, out of 16 subjects, only 2 dropped out in agreement with the literature that consistently supports tolerability of serial ketamine infusions. However, if risk of dropping out due to assessment burden occurs, subjects will have the option of completing a minimum core of primary outcome measures and maintain a flexible routine for recurrent appointments. For missing values, we will handle it by data imputation strategies, by last-

observation-carried-forward, and by the exclusion of dropouts (completers-only analyses); 3) Lost of follow-up: We would initiate outreach procedures and safety checks.

E. STUDY COMPENSATION

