Participants will be compensated for completing the assessment sessions throughout the study. Assessment sessions involve individual clinical interviews, self-report, and semi-structured questionnaires. Compensation for assessment sessions will be delivered according to the following schedule: \$75 for Eligibility Screen and Baseline (1 week prior to starting treatment, approximately 3 hours), \$50 for each assessment during medication phase (total of 03 over 3 weeks; +/- 02 hrs. each), \$30 at post-ketamine PE sessions 4, 6, 8 and 12 (total of 04 over 2 months; +/- 02 hrs. each), and \$30 for monthly follow-up post-treatment (twice for +/- 02 hrs.) for a total of up to \$405. Participants who prematurely withdraw from study assessments will not be compensated for assessment sessions that have not yet taken place.

F. BIBLIOGRAPHY AND CITED REFERENCES

Abdallah, C. G., Adams, T. G., Kelmendi, B., Esterlis, I., Sanacora, G., & Krystal, J. H. (2016). KETAMINE'S MECHANISM OF ACTION: A PATH TO RAPID-ACTING ANTIDEPRESSANTS. *Depress Anxiety*, 33(8), 689-697. doi:10.1002/da.22501

Abbott, C. S., Lim, K. O., Forbes, M. K., Erbes, C., Tye, S. J., Grabowski, J. G., . . . Shiroma, P. R. (2018). Efficacy, Safety, and Durability of Repeated Ketamine Infusions for Comorbid Posttraumatic Stress Disorder and Treatment-Resistant Depression. *J Clin Psychiatry*, 79(3). doi:10.4088/JCP.17m11634

Abbott, C. S., Shiroma, P. R., Cullen, K. R., Johns, B., Thuras, P., Wels, J., & Lim, K. O. (2017). The Antidepressant Effect of Repeat Dose Intravenous Ketamine Is Delayed by Concurrent Benzodiazepine Use. *J Clin Psychiatry*, 78(3), e308-e309. doi:10.4088/JCP.16l11277

Aldrete, J. A. (1995). The post-anesthesia recovery score revisited. *J Clin Anesth*, 7(1), 89-91.

Averill, L. A., Purohit, P., Averill, C. L., Boesl, M. A., Krystal, J. H., & Abdallah, C. G. (2017). Glutamate dysregulation and glutamatergic therapeutics for PTSD: Evidence from human studies. *Neurosci Lett*, 649, 147-155. doi:10.1016/j.neulet.2016.11.064

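### The urine pregnancy test is scheduled only at baseline, so infusions 2 and 3 rest on a result about 1-2 and 2-3 weeks old unless the infusion SOP adds a test

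*Combined protocol and SAP*

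**What the plan says.** Table 3 (D.3.1) excludes "pregnancy (confirmed by lab test") and also excludes women who cannot or will not use accepted contraception while in the study. A positive urine drug screen is a further exclusion.

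D.5.1 says of the Eligibility and Baseline Assessment: "A urine pregnancy, if applicable, and drug screen will also be obtained". That assessment "will be accomplished during 1-2 visits over a 7 -day period prior to starting treatment".

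Table 5 has the row "Physical Exam/ECG/Pregnancy test/Urine toxicology" under its infusion safety heading, with one mark, in the baseline column. The other rows under that heading (mAldrete; CADSS, BPRS+ and YMRS) are marked in the treatment column. D.5 presents Table 5 as the summary of all assessments, including those made at each infusion.

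D.1 describes a "3-week ketamine-PE phase composed by weekly single intravenous ketamine". For infusion days, D.4.1 and Table 4 list fasting, catheter placement, vital signs, CADSS, BPRS+, YMRS and mAldrete. Neither urine test appears there or among the treatment assessments in D.5.2. D.4.1 says that an SOP for the infusions is attached; it is not part of the public document.

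**The concern.** The reason for excluding a pregnant woman at entry applies equally at the second and third doses. A single baseline test can miss a pregnancy in two ways: conception may be too recent to show, or it may happen afterwards. Required contraception lowers the chance of the second but detects neither. The vital signs and rating scales taken before each infusion do not test for pregnancy. Staff could therefore follow the printed schedule exactly and give infusion 2 or 3 to a woman who would have been excluded at entry. What is at stake is avoidable exposure to ketamine during pregnancy; no estimate or conclusion of the trial depends on it.

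**Working it through.** The plan states no maximum age for the test result, so there is no figure of its own to reproduce. The age follows from the schedule.

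**Inputs**
- Infusions are weekly, three in all (D.1). No visit windows are given, so exact 7-day spacing is assumed: days 0, 7 and 14.
- Let L be the number of days from the baseline test to infusion 1. D.5.1, the only text that times the urine tests, gives L = 0 to 7.
- D.1 has eligible patients "Those who meet eligibility criteria will complete baseline assessment one week prior to starting treatment", and section E describes "Eligibility Screen and Baseline (1 week prior to starting treatment, approximately 3 hours"). Both give L = 7, the upper end of the D.5.1 window.
- Section 6.7.3 puts the CAPS-5 "at baseline (1-2 weeks prior to starting the intervention), week 4" and at week 12. The Table 5 baseline column is also headed 1-2 weeks. Read as lead time, these give L = 7 to 14.

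**Formula**

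Age of result at infusion k = 7 × (k − 1) + L days.

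| Infusion | D.5.1 window (L = 0-7) | D.1 and section E (L = 7) | 1-2 weeks read as lead time (L = 7-14) |
|---|---|---|---|
| 1 | 0-7 days | 7 days | 7-14 days |
| 2 | 7-14 days | 14 days | 14-21 days |
| 3 | 14-21 days | 21 days | 21-28 days |

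If a test on the day of infusion 1 is not allowed, L starts at 1, and the lower ends in the D.5.1 column become 1, 8 and 15 days.

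**Which column applies.** D.5.1 is the section that orders the urine tests, and D.1 and section E fit inside its window. The wording in 6.7.3 concerns the CAPS-5. The Table 5 header stands beside Week 1 to 12 and 2 months, so it may describe the length of the baseline period rather than lead time. The supported figures are therefore about 1-2 weeks at infusion 2 and 2-3 weeks at infusion 3.

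**Is the baseline-only reading safe?** Column positions in Table 5 could be distorted by text extraction. D.5.1 places the test at baseline independently, and D.4.1, Table 4 and D.5.2 contain no repeat, so the reading does not depend on the table layout.

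**The case against.** The strongest objection is the unseen SOP. A same-day test could well be set out there, in which case no woman goes untested and only the tables are incomplete. This stands: the gap is shown in the protocol text, not in practice.

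Second, Table 3 sets entry criteria, and the plan nowhere promises to re-verify them. A reader might infer an internal contradiction; there is none. Testing at entry plus required contraception, over a dosing phase of 14 days from first to last infusion, is a defensible choice. What remains is that contraception does not detect a pregnancy and that a repeat test costs little.

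Three stronger readings are tempting and are not supported:
- That the result is 4 weeks old at infusion 3. This needs the Table 5 header to mean lead time, or the CAPS-5 wording to govern urine tests.
- That 20 of the 30 planned infusions (10 × 2 of 10 × 3) are affected. That count covers all patients, whereas the pregnancy test concerns only some women, whose number is not given.
- That D.6.2 makes drug use after baseline a bar to dosing. D.6.2 calls ketamine contraindicated for listed diagnoses, including a substance use disorder within 6 months of initial assessment. That is a diagnosis made at entry, not an episode of later use. A repeat drug screen can rest only on the Table 3 entry criterion.

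**Conclusion.** The point holds as a minor gap in safety scheduling. On the public text, the only scheduled pregnancy result is 7-14 days old at infusion 2 and 14-21 days old at infusion 3, and a pregnancy that becomes detectable in between would not be found before dosing. This assumes exact weekly infusions, the D.5.1 window, and an SOP that does not already require a test. Late infusions would make the result older.

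No probability of a missed pregnancy can be given: the documents state neither a pregnancy rate nor the number of applicable women, which may be zero among 10 patients. It would be wrong to infer that pregnant women will be dosed. The sample size and the descriptive analysis are unaffected.

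**What to change.** First check the attached infusion SOP. If it already requires a pre-dose pregnancy test, only align Tables 4 and 5 with it.

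If it does not, add a urine pregnancy test for women to whom it applies, at t0 − 60 min before infusions 2 and 3, to Table 4 and to the treatment column of Table 5. Add it before infusion 1 as well if the baseline test was not done within the 7-day window. Read the result before dosing and withhold ketamine if it is positive. The same entry should say whether a woman who tests positive continues PE and the week 12 assessment, since the text gives no instruction for this.

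The cost is two urine tests per applicable woman, or three if infusion 1 needs one, at visits that already have an assessment at that time. An occasional infusion may be postponed, and its PE session moves with it because PE follows within 24 hours.

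A repeat urine drug screen at the same time point is optional. For infusions 2 and 3 it would mean at most 10 × 2 = 20 screens.
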